b) List of any other medical device or medication to be used during the clinical investigation if not already specified in the instructions for use.

Not Applicable - No additional medical devices or medications are intended for use in this clinical investigation beyond what is already specified in the Instructions for Use (IFU) for the Obi Gen 3 Medical Robotic Feeding Device.

c) Number of investigational devices to be used, together with a justification.

This usability study will use ten (10) production-equivalent Obi-Gen 3 devices. The study sponsor, DESIN LLC, is providing these devices, which represent final design units intended for validation prior to broader commercialization.

The selected number is justified based on the following factors:

- The study will enroll approximately 55–60 participants across three key stakeholder groups: providers, caregivers, and patients.
- The study design includes a 1-week device trial per patient-caregiver dyad, during which each device will be rotated and re-used among participants.
- Cleaning and infection control protocols will be implemented between uses to ensure participant safety and device integrity.
- This number allows for redundancy and replacement should a device require maintenance or become damaged during the study.
- The Obi Gen 3's limited-risk profile (FDA and MDR Class I classification) supports the re-use of devices across participants, provided proper decontamination procedures are followed.
- It also ensures sufficient device availability for logistics coordination, shipping, training support, and concurrent participation at different study locations.

This approach balances scientific rigor, operational feasibility, and resource efficiency while supporting timely and representative data collection for design validation purposes.

A.6.3. Subjects

a) Inclusion Criteria for Subject Selection

Participants will be recruited from three key stakeholder groups—providers, caregivers, and patients—who represent the intended users of the Obi Gen 3 Medical Robotic Feeding Device. Inclusion criteria are as follows:

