Each subject's participation in the clinical investigation will vary based on their role (provider, caregiver, or patient) and level of engagement. The core duration of participation for all enrolled stakeholders is approximately one week, corresponding to the required trial period of the Obi Gen 3 Medical Robotic Feeding Device in a home, school, or community setting.

- **Patients and Caregivers:** Participants are expected to use the device for at least five meals over a one-week period. During this time, they will use the device in real-life contexts and later complete post-trial surveys and optional follow-up interviews.
- **Providers:** Participating providers are expected to conduct an initial in-office assessment to determine patient suitability for the Obi Gen 3, recommend at least one patient for trial use, and provide feedback based on their clinical observation. Their involvement also includes completing a usability survey post-trial and, if applicable, participating in a brief follow-up interview.

Follow-up through telephone-based semi-structured interviews may be conducted within one month to further clarify or expand responses to open-ended questions. These interviews will be scheduled within one month of the trial's completion.

h) Number of subjects required to be included in the clinical investigation, and where needed, anticipated distribution of enrolment among the participating investigation sites.

A total of 60 participants will be recruited using flyers and word-of-mouth strategies

Stakeholder Group	Target Sample Size
Providers [Occupational Therapists (OTs), Assistive Technology Professionals (ATPs), Speech Language Pathologists (SLPs), and other relevant providers)	20 in various practice settings
Caregivers (family members, aides, support personnel)	20 (5 for adults, 15 for children)
Patients (adults and children using Obi Gen 3)	20 (5 adults, 15 children)

i) Estimated time needed to select this number (i.e. enrolment period).

The estimated time required to enroll the whole sample for this usability study is 4–5 weeks, given the study's targeted outreach strategy, electronic recruitment methods, and existing professional and caregiver networks available to DESIN LLC and the investigative team. Recruitment materials, including flyers and direct outreach, will be distributed electronically and through participating service providers to expedite enrollment.

j) Relationship of investigation population to target population.

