Given the short duration and minimal risk nature of this usability study, the expected drop-out rate is anticipated to be low (less than 10%). Participants will be engaged for a one-week home or community-based trial of the Obi Gen 3 device,. The limited time commitment, non-invasive nature of participation, and flexibility of remote data collection (via Qualtrics and telephone interviews) are expected to support high retention.

Potential reasons for early withdrawal or loss to follow-up may include:

- Lack of interest or time to complete the trial period or follow-up activities
- Health-related issues or changes in caregiving responsibilities
- Technological issues or accessibility barriers (e.g., inability to access electronic surveys)
- In rare cases, discomfort or dissatisfaction with the device

Because the study does not involve treatment, diagnostic procedures, or invasive interventions, death is not anticipated and is not an endpoint. Any withdrawal or loss to follow-up will be documented with reason, when available. Data collected prior to withdrawal will be included in the analysis, consistent with an as-treated approach.

f) The rationale for the number of procedures to be performed by a single user as part of the learning curve and how these data are to be analysed, if applicable.

Given that this investigation evaluates the usability of a robotic feeding device designed for individuals with upper extremity impairments, caregivers, and providers, it is important to account for the initial learning period associated with device setup, operation, and integration into daily routines. The one-week trial period with a minimum expectation of five completed meals per patient/caregiver dyad is designed to reflect a realistic and sufficient exposure to allow users to become familiar with the device and overcome early learning curve effects.

This threshold was selected based on preliminary feedback from internal evaluations and stakeholder consultations, which indicated that users typically require **3–5 sessions**, to feel comfortable with basic functions (e.g., powering on, positioning the spoon, switching food compartments). For providers, the requirement to recommend and assess at least one patient supports evaluation of the device within their existing workflow, allowing observation of setup, training, and follow-up in a practical setting.

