Although this study does not include formal repeated-measures testing or time-stamped use logs, reported experience over multiple uses (i.e., across several meals and settings) will provide insight into how effectively users can learn to operate the device independently. This data will inform training recommendations and design refinements to support intuitive, low-burden use in real-world environments.

g) Pass/fail criteria to be applied to the results of the clinical investigation.

As a design validation study, the primary objective of this clinical investigation is to determine whether the Obi Gen 3 production equivalent device meets its formally documented user needs and intended use across three key stakeholder groups: patients, caregivers, and providers. The pass/fail criteria are based on usability outcomes aligned with ISO 13485 and FDA design validation requirements. The following criteria must be met for the device to be considered as having “passed” the clinical investigation:

Primary Endpoints: Acceptance criteria is based on safety and quality risk (see IFD-DES-054-1, Design Validation Plan, and IFD-DES-054-2, Design Validation Protocol). Note: Design Validation planning involves more than just human subject testing. This CIP covers only the human subject portion.

Intended Use: For all subjects that complete the 1-week trial, the following must be met:

- ICF performance qualifier for Functional Eating must drop at least one severity level (ex. “severe” to “moderate”) for 85% of patients.
- No Serious Adverse Device Effects (SADE), Serious Health Threat, or Unanticipated Serious Adverse Device Effect (USADE).

User Needs: For all subjects that complete the 1-week trial, 50% of respondents must be in favor that the requirement has been fulfilled (see IFD-DES-051-1 Validation Plan)

If the investigation meets or exceeds these thresholds across all stakeholder groups, the design will be deemed to have passed and is considered validated. If one or more criteria are not met, the results will be analyzed to determine if design modifications, additional training resources, or workflow adjustments are necessary prior to commercialization.

h) The provision for an interim analysis, criteria for the termination of the clinical investigation on statistical grounds, where applicable.

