Given the usability-focused, non-interventional design of this clinical investigation, the approach to managing missing, unused, or spurious data will prioritize transparency, traceability, and context-based interpretation rather than imputation or statistical correction.

Missing Data - All efforts will be made to minimize missing data by:

- Using structured and user-friendly electronic data collection tools (Qualtrics),
- Providing reminders for survey completion, and

- Offering support to participants during the trial period.

When data are missing, the specific nature and reason for the missing information (e.g., participant withdrawal, technical issues, non-response) will be recorded in the study database. Missing data will not be imputed, as the primary goal is descriptive analysis rather than inferential statistical modeling. Analyses will be conducted using available data only, and the extent of missingness will be reported for each data element.

Unused or Incomplete Data - Incomplete survey responses or interviews that do not meet minimal content thresholds (e.g., <50% of questions answered) may be excluded from individual item-level analysis but will be retained in the dataset for auditability. The rationale for excluding such data will be documented in the data analysis plan and in the final study report.

Spurious or Implausible Data - Any values that are clearly spurious (e.g., internal inconsistencies, out-of-range responses) will be flagged during data quality checks. If these data cannot be resolved through source verification (e.g., interview notes, metadata review), they will be excluded from analysis and annotated accordingly in the dataset with justification.

Participant Drop-outs - Participants who withdraw from the study after enrollment will be asked, if willing, to provide a brief reason for withdrawal. Drop-outs will be tracked, and their status will be clearly documented in the final dataset. Data collected prior to withdrawal will be included in the analysis unless the participant requests removal of their data per the informed consent agreement. The rate and pattern of drop-outs or early discontinuation will be described in the final study report to assess potential biases or operational challenges affecting the usability evaluation.

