n) Exploratory analysis and sensitivity analysis (e.g. to explore robustness of results of primary and secondary analysis with respect to different methods used for handling missing data), if applicable.

Not applicable. This study is concerned with qualitative insights and limited scope of variables.

o) Procedures for reporting any deviation(s) from the original statistical analysis plan.

Any deviation from the original statistical analysis plan (SAP), whether related to the analysis population, analytical methods, handling of missing data, or presentation of results, will be documented in the protocol deviation log and addressed in the final clinical investigation report.

If deviations are necessary during the course of data analysis—such as the inclusion of alternative summary measures, subgroup analyses not originally specified, or adjustments to account for unforeseen data collection challenges—these will be:

- Clearly documented with a justification for the change,

- Dated and signed by the responsible investigator or data analyst,
- Reviewed by the principal investigator and, if applicable, the sponsor, and
- Reported transparently in the final report, along with the impact of the deviation on the interpretation of the study outcomes.

All such deviations will be made prior to unblinding or final data lock to ensure analytical integrity and avoid bias in interpretation. Because this is an exploratory usability study using descriptive and qualitative methods, formal pre-specification of statistical hypotheses is limited; however, the principles of transparency, traceability, and justification will be upheld for any post hoc analytical decisions.

p) For multicentre clinical investigations, a strategy for handling the potential imbalance of the numbers of subjects across investigation sites.

Not applicable. This study involves a single site.

q) A strategy for pooling data, if applicable.

Not applicable based on the study design.

A.8. Data Management

a) Methods (e.g. CRF) for data entry and collection.

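### Sensitivity analysis is ruled out on the ground that the study is qualitative, yet validation is decided by two proportions that one or two missing outcomes can reverse in groups of about 20

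*Protocol*

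**What the plan says.** Section A.7 n) of the protocol asks for exploratory and sensitivity analysis and names robustness to missing-data handling as its example. The whole answer is "Not applicable. This study is concerned with qualitative insights and limited scope of variables".

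Section A.7 g) sets the pass/fail criteria. For intended use, "ICF performance qualifier for Functional Eating must drop at least one severity level" "for 85% of patients" (ICF here is the functioning classification, not the consent form). For user needs, half of the respondents must be in favour. Both criteria are restricted to people who complete the one-week trial. If they are met, together with a safety criterion, the design counts as validated.

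On missing data, section A.7 m) states "Analyses will be conducted using available data only", with no imputation. Surveys below a content threshold, for which under half of the questions answered is only an example, "may be excluded from individual item-level analysis but will be retained in the dataset for auditability". The same section promises to report the extent of missingness for each data element, the rate and pattern of drop-outs, and the rationale for excluding surveys.

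Section A.6.3 c) i) provides that people who cannot use the device safely or effectively at first use are withdrawn. Section A.7 e) 6) says that "the expected drop-out rate is anticipated to be low (less than 10" per cent.

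**The concern.** The reason given in A.7 n) is not true of this plan. A yes/no validation decision taken from two percentages is a quantitative decision, even though the study plans no hypothesis test and gathers much qualitative material besides.

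Three rules take people out of the denominators of those percentages. The completer restriction removes anyone who stops early, including those withdrawn because the device did not work for them. The available-data rule removes completers with no recorded outcome. The survey rule can remove a user-needs item that was answered because other items in the same survey were blank. This last rule also sits badly with A.7 a), which says that all available data from each stakeholder group go into the final analysis.

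At stake is whether a validation claim that rests on about 20 people per group would change if a few absent people were counted. The plan declines in advance to look.

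**Working it through.** **Inputs.** Patients: 20, and 20 in each other group, so 3 × 20 = 60 (A.6.3 h). Section A.6.2 c) gives total enrolment more loosely: "The study will enroll approximately 55–60 participants across three key stakeholder groups: providers, caregivers, and patients". A group may therefore end below 20. Thresholds: 85% and 50% (A.7 g), read as at least. Drop-out: below 10% (A.7 e) 6). The protocol derives no sample size from these criteria, so there is no calculated figure to reproduce.

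**Thresholds as counts**, rounding threshold × n up:
- 85%: 17 of 20, 17 of 19, 16 of 18.
- 50%: 10 of 20, 10 of 19, 9 of 18.

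**Bounds.** Let N be the number who started, m the number with a missing outcome, and k the favourable outcomes observed. The plan computes k/(N − m). The bounds are k/N (all missing unfavourable) and (k + m)/N (all missing favourable).

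| Rule | N | m | Observed | Missing unfavourable | Missing favourable |
|---|---|---|---|---|---|
| 85% | 20 | 2 | 16/18 = 88.9%, pass | 16/20 = 80.0%, **fail** | 18/20 = 90.0%, pass |
| 85% | 20 | 2 | 15/18 = 83.3%, fail | 15/20 = 75.0%, fail | 17/20 = 85.0%, **pass** |
| 85% | 20 | 1 | 17/19 = 89.5%, pass | 17/20 = 85.0%, pass | 18/20 = 90.0%, pass |
| 85% | 20 | 1 | 16/19 = 84.2%, fail | 16/20 = 80.0%, fail | 17/20 = 85.0%, **pass** |
| 85% | 19 | 1 | 16/18 = 88.9%, pass | 16/19 = 84.2%, **fail** | 17/19 = 89.5%, pass |
| 50% | 20 | 2 | 9/18 = 50.0%, pass | 9/20 = 45.0%, **fail** | 11/20 = 55.0%, pass |
| 50% | 20 | 2 | 8/18 = 44.4%, fail | 8/20 = 40.0%, fail | 10/20 = 50.0%, **pass** |
| 50% | 20 | 1 | 10/19 = 52.6%, pass | 10/20 = 50.0%, pass | 11/20 = 55.0%, pass |
| 50% | 20 | 1 | 9/19 = 47.4%, fail | 9/20 = 45.0%, fail | 10/20 = 50.0%, **pass** |
| 50% | 19 | 1 | 9/18 = 50.0%, pass | 9/19 = 47.4%, **fail** | 10/19 = 52.6%, pass |

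Bold marks a reversed verdict. The rows with 17/19 and 10/19 are the lowest observed passes at N = 20 with one missing. Both survive, so in that case no pass can become a fail.

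**Against the expected drop-out.** Below 10% of 20 means at most one person in a group. Below 10% of 60 means at most five in the study, and two of these could fall in one group. The protocol does not state the rate per group. At N = 19, one missing is 1/19 = 5.3%.

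**How often a result lands in the reversible zone (85% rule, N = 20).** The protocol gives no expected improvement rate, so a range is assumed. With two missing, the reversible results are k = 15 and k = 16, and the probability is P(K = 15) + P(K = 16) for K binomial(18, p). With one missing, the only such result is k = 16, for K binomial(19, p).

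| Assumed true rate p | Two missing: 15 or 16 of 18 | of which 16 of 18 (a pass that could fail) | One missing: 16 of 19 |
|---|---|---|---|
| 0.80 | 0.40 | 0.17 | 0.22 |
| 0.85 | 0.50 | 0.26 | 0.24 |
| 0.90 | 0.45 | 0.28 | 0.18 |
| 0.95 | 0.22 | 0.17 | 0.05 |

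**The case against.** The strongest reply is that A.7 g) defines the criteria among completers. Someone who leaves early is then outside the population and is not a missing value within it, so 16/20 is not the protocol's own criterion. That is correct. It means that a remedy must say who counts as missing, and that the table should support the completer result and not replace it. It does not make A.7 n) true, and completers with no recorded outcome or an excluded survey remain missing even on the protocol's definition.

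A second reply is that the detail may sit in an analysis plan that is not shown. That would answer a silence, but here the protocol states that the analysis is not applicable.

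Some stronger readings are tempting and are not supported:
- A reader might infer that a single missing patient at the planned size of 20 could turn a failing device into an observed pass. It cannot, since 17/20 and 10/20 still pass. That direction needs two missing, or fewer than 20 enrolled.
- A reader might infer that the report would hide the problem. A.7 m) commits to reporting missingness, drop-out pattern and exclusion rationale, and from full counts a reader could work out the bounds.
- A reader might infer that dissatisfied users are the likeliest to be missing. A.7 e) 6) lists discomfort or dissatisfaction as a rare reason only, and nothing in the protocol ranks non-responders. Reminders and a gift card are also planned. The link to outcome is explicit only for people withdrawn because they could not use the device.
- A reader might infer that the survey exclusion threatens the 85% rule. The protocol does not name the source of the qualifier. Functional feeding status is recorded on the needs-assessment form, part of which providers complete at follow-up, so the exclusion can be tied only to the 50% rule.

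**Conclusion.** The concern holds in a limited form. A.7 n) gives a reason that A.7 g) contradicts, and the plan contains no check that the validation verdict survives missing or excluded outcomes. With 20 in a group, two missing outcomes can reverse either criterion in either direction. One missing outcome can reverse only an observed fail. With 19 in a group, one missing outcome can overturn a pass on either criterion.

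The sizes rest on three assumptions: the 50% rule is applied within each stakeholder group, as the requirement that thresholds be met across all groups suggests; the denominators of 19 and 20 count everyone who started; and the probabilities use assumed improvement rates, with a given number missing and independent outcomes. The bounds are extremes and do not predict how absent people would have fared. The point should be corrected before the data are analysed, but it does not undermine the design.

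**What to change.** Replace the text of A.7 n) with a supportive table placed beside the completer result of A.7 g). It repeats each pass/fail proportion over all enrolled participants in the relevant group who started the trial, including those withdrawn after initial use. Missing outcomes are counted first as not improved or not in favour, then as improved or in favour, and the table states whether the verdict changes. For providers, who do not take the device home for a trial, the text should define what counts as having started.

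In A.7 m), keep every answered user-needs item in that item's denominator, and delete the discretionary exclusion for the items that feed the pass/fail decision.

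The cost is one table and a few sentences, with no imputation model, hypothesis test or extra participants. The drawback for the sponsor is that the verdict may have to be reported as sensitive to missing data.

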Devices used in during the study will be returned to DESIN LLC, visually inspected, functionally evaluated, cleaned, disinfected and otherwise reconditioned as needed in accordance with DESIN LLC's SOP120. These devices will then be approved to enter the company's trial device fleet. These devices will be used with new prospective customers.

A.6.5 Monitoring Plan

General outline of the monitoring plan to be followed, including access to source data and the extent of source data verification planned.

There is no official monitoring plan developed. However, to ensure adequate monitoring of the study, the principal investigator and/or study team shall cooperate with DESIN LLC. This includes, but is not limited to, allowing the assessment of facilities utilized for this study, providing access to subject report forms, and subject medical records reasonably requested.

A.7. Statistical Design and Analysis

With reference to A.5 and A.6, the description of and justification for statistical design and analysis of the clinical investigation shall cover the following.

a) Analysis population (e.g. intention-to-treat, per-protocol, as-treated) and procedures that take into account all the data.

This clinical investigation is a non-randomized, non-comparative, mixed-methods usability study intended to evaluate whether the production equivalent Obi Gen 3 robotic feeding device meets the documented user needs and intended use across stakeholder groups. As such, the primary focus of the statistical design is on descriptive and qualitative analysis rather than hypothesis testing or inferential statistics.

All participants who complete informed consent and the survey be included in the analysis population. Given the non-interventional nature of the study, the analysis will follow an as-treated approach, with all available data from each stakeholder group included in the final analysis. Participants who after consent but before completing any trial procedures will be excluded from the analysis population. Missing data will be documented but not imputed, as the primary intent is to assess observed usability and feedback trends.

b) Descriptive statistics of baseline data, treatments, safety data and where applicable, primary and secondary endpoints.

Descriptive statistics will be used to summarize:

- Baseline demographic and clinical characteristics, including age, gender, diagnosis, and prior experience with assistive technology.

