Interim reports and updates may also be provided to stakeholders or sponsors as needed during the course of the investigation. A final report or closure notification will be submitted to the IRB and sponsor upon completion or early termination of the study. This will include a summary of the study conduct, data collected, participant outcomes, and any relevant findings or deviations.

d) Corrective and preventive actions and principal investigator disqualification criteria.

DESIN LLCs maintains SOP080, CAPA Procedures. CAPAs are triggered based upon a risk assessment. If there is a suspected issue with the CIP surpassing the calculated risk threshold, corrective and preventive action procedures will be triggered per DESIN LLCs quality system procedure SOP080, CAPA Procedures.

For final analysis, subjects who have major protocol deviations will not be included in the statistical analysis of the “per-protocol” population.

A.11. Device Accountability

a) Description of the procedures for the accountability of investigational devices as specified in 7.9;

This study will use production equivalent/production candidate devices, which have been constructed in accordance with DESIN LLC's Quality Management System production controls. Accordingly, each unit of Obi will be labeled as a "study device" identified by a model number, lot number and date. A device accountability log will be maintained in accordance with the company's SOP220, Trial Assessment Procedure. This procedure includes processes for documenting dates of receipt, use, return of the device, the device lot number, and the subject number for whom the device was shared with. This process will be maintained until the conclusion of the study.

b) Procedures and particular materials and instructions for the safe return of investigational devices, including those that are potentially hazardous.

In the event of suspected or confirmed device deficiency, or adverse event, the device must be returned to DESIN LLC for investigation in accordance with its SOP120, Return and Service Procedures.

Complaints will be logged per D-FRM-005, Complaint Form per SOP120. Coordinating with the subject for returning the device will be conducted by DESIN LLC.

A.12. Statements of Compliance

a) Statement specifying that the clinical investigation shall be conducted in accordance with ethical principles that have their origin in the Declaration of Helsinki

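### The analysis sets are inconsistent, and the completer-only pass/fail denominator leaves out first-use failures and serious device effects in early stoppers

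*Protocol*

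**What the plan says.** Three places in the protocol bear on who is counted.

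- **A.7 a), analysis population:** "the analysis will follow an as-treated approach, with all available data from each stakeholder group included in the final analysis". The same paragraph gives a membership rule: "All participants who complete informed consent and the survey be included in the analysis population". On withdrawals, A.7 e) 6) adds: "Data collected prior to withdrawal will be included in the analysis, consistent with an as-treated approach". A.7 m) says the same, unless the participant asks for removal.
- **A.7 g), pass/fail criteria:** the 85% functional-eating rule and the no-serious-device-event rule both stand under "Intended Use: For all subjects that complete the 1-week trial, the following must be met". The user-needs rule repeats the restriction: "For all subjects that complete the 1-week trial, 50% of respondents must be in favor".
- **A.10 d), corrective and preventive actions:** "For final analysis, subjects who have major protocol deviations will not be included in the statistical analysis" of the per-protocol population. In A.7 a) the term per-protocol occurs only among the examples in the item heading; the text beneath chooses as-treated.

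Four other sections matter. A.6.3 c) i) withdraws patients found unable to use the device safely or effectively at first use. A.6.4 a) plans the follow-up office assessment for those who complete the trial. A.14 f) collects safety events from consent signature to study completion. A.7 n) declares sensitivity analysis not applicable. No section ranks or reconciles the three sets.

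**The concern.** A.7 g) decides whether the design counts as validated. Its denominator is conditional on finishing the week, and not finishing is partly a consequence of the device not suiting the patient. The patients whom A.6.3 c) i) expects to withdraw on or near the first day are the clearest evidence against fulfilment of the intended use, yet they leave the count. A serious device effect that makes someone stop early also falls outside the wording of the safety criterion.

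A.7 a) points the other way by keeping all available data, and A.10 d) mentions a third set for the final analysis. With 20 patients the sets need differ by only one or two people to change the verdict, and no planned analysis would show that it depends on the set.

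**Working it through.** The plan has no derived figure to reproduce. The total of 60 is 20 + 20 + 20, supported by a quoted minimum of 15 per user group, and no formal test is planned. The check is therefore a comparison of the sets followed by exact counting.

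**Step 1. Who falls in which set**

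| Participant | A.7 a), e) 6), m) | A.7 g) | A.10 d) per-protocol |
|---|---|---|---|
| Completer, no major deviation | in | in | in |
| Completer with a major deviation | in | in | out |
| Patient withdrawn at first use | data kept, although A.7 a) also asks for a completed survey | out | not stated |
| Early stopper with a serious device effect | data kept; event collected under A.14 f) | out | not stated |

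**Step 2. Inputs from the protocol.** 20 patients (A.6.3 h); thresholds of 85% and 50%, to be met or exceeded (A.7 g); expected drop-out below 10% (A.7 e) 6). The numbers of withdrawals, deviators and improvers below are illustrative assumptions.

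**Step 3. Improvers needed,** 0.85 × n rounded up:

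- n = 20: 17.00, so 17 (three non-improvers allowed)
- n = 19: 16.15, so 17 (two allowed)
- n = 18: 15.30, so 16 (two allowed)
- n = 17: 14.45, so 15 (two allowed)

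**Step 4. Completers against all starters,** counting withdrawals as not improved (a rule that the protocol does not contain):

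- One withdrawal: 17/19 = 89.5% and 17/20 = 85% both pass; 16/19 = 84.2% and 16/20 = 80% both fail. The verdict does not change.
- Two withdrawals: 16/18 = 88.9% passes; 16/20 = 80% fails.
- Three withdrawals: 15/17 = 88.2% passes; 15/20 = 75% fails.

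Two of 20 is 10%, at the edge of the drop-out that the protocol expects overall.

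**Step 5. Completers against per-protocol** (no imputation rule needed):

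- 15/18 = 83.3% fails; with one measured non-improver excluded, 15/17 = 88.2% passes.
- In reverse, 17/20 = 85% passes; with one improver excluded, 16/19 = 84.2% fails.

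**Step 6. User needs.** 9/18 = 50% passes among completers. If two people who did not complete return unfavourable surveys, 9/20 = 45% fails.

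**Step 7. Serious device events.** One such event in an early stopper gives 0 among completers (pass) and 1 among everyone exposed (fail).

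**The case against.** The strongest defence is that nothing truly conflicts: A.7 a) sets a general reporting population, A.7 g) states one specific denominator for the acceptance criteria, and the full A.10 d) sentence says only who is outside a per-protocol set. Several parts of this stand.

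- A reader might infer that A.10 d) removes major deviators from the 85% and 50% counts. The text does not say so: no section ties the per-protocol set to either threshold. Step 5 shows what would follow if the set were used that way, not what the plan prescribes.
- A reader might also infer that exclusions would be chosen after outcomes are seen and would raise the pass rate. The documents do not establish this. A.10 b) requires prompt recording of deviations, though it sets no time for grading them, and Step 5 shows that the rate can move either way. Patients with missed visits would usually have no follow-up rating, so they would not be measured non-improvers.
- The absence of a definition of a major deviation is a detail that a statistical analysis plan may supply, and is not relied on here.
- For the 85% rule, the as-treated and completer sets may coincide in practice, because the planned follow-up assessment is for completers and nothing is imputed. Step 4 therefore needs an added rule for withdrawals.

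The defence does not remove the problem with the completer rule itself. Followed as written, that rule takes first-use failures and early serious device effects out of the verdict while other sections keep those data. Safety reporting under A.14 would still apply to such an event, but the pass criterion as worded would not count it.

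**Conclusion.** The point holds as an inconsistency within the protocol, with its main consequence in A.7 g). The validation verdict is conditional on completion, contrary to the all-data principle of A.7 a), and the role of the per-protocol set is left open. At 20 patients, two withdrawals counted as not improved, one measured non-improver excluded, or one serious device effect in an early stopper is enough to change a criterion's result. One withdrawal alone does not change the 85% result. These results rest on assumed counts and, for withdrawals, on an assumed scoring rule. They show sensitivity and do not predict an outcome. No claim is made that the exclusions are intended to favour the device, or that they would always do so. The matter should be corrected before data are opened, because the thresholds decide whether the design is deemed validated.

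**What to change.** 1. In A.10 d), delete the per-protocol sentence, or label that set supportive only and state that deviations are graded before outcome data are opened.
2. Reconcile A.7 a) and A.7 g) by naming one primary set for each criterion:
   - patients and caregivers: all who consented and started the home trial, with a stated rule for those without a follow-up rating (for example, counted as not improved, with the completer result shown alongside);
   - providers, who do not undertake the home trial themselves: all who consented and assessed at least one patient;
   - serious device events: everyone exposed to the device.
3. In A.7 a), reconcile the survey-completion condition with the statements in A.7 e) 6) and A.7 m) that data collected before withdrawal are kept.

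This concerns only who is counted; the withdrawal rule in A.6.3 c) i) is not touched. The cost is protocol wording, alignment with the Design Validation Plan on which A.7 g) bases its acceptance criteria, and a stated pass rate that may be slightly less favourable.
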